## Figure Showing Key Analysis Sets From CS3B

The figure below shows the number of participants in the ITT/Safety set and efficacy sets for the CS3B.

Product: Nusinersen	Statistical Analysis Plan
Study: 232SM203	Version: 3.0 Final

Summary of analysis sets from CS3B

## Summary of How Historical Data Will be Used in the Analysis

The enrollment criteria of the Part B infantile-onset in 232SM203 has been designed to be similar to CS3B study (external data). In general, consistent inclusion/exclusion criteria have been utilized and efficacy assessments at the same timepoints have been included.

As part of the analysis of the 232SM203 study the external data will be utilized for the following purposes:

- For the primary and secondary endpoints comparing to sham, the higher dose participants from 232SM203 will be compared to matched sham control participants from CS3B. Comparability will be assessed for 232SM203 compared to CS3B sham based on key covariates and a matching algorithm will be utilized to select at least 20 CS3B sham control subjects. For the remaining secondary endpoints, the high dose participants will be compared to 12 mg dose using the 232SM203 ITT population.
- Use of the group of matched control subjects described in the first bullet for summaries of safety endpoints. This is in order to provide a reference group of participants with similar disease who have not undergone lumbar puncture SMA.

## 3. Definitions

## 3.1. Dates and Points of Reference

• Study Day 1: the date of the first dose of study treatment in 232SM203

Note: Efficacy sets defined as subjects with the opportunity to attend the visit if the study had not stopped due to efficacy.

- Study Day
  - $\circ$  For a date on or after Study Day 1

Study Day = (Date of Interest) - (Study Day 1) + 1

o For a date before Study Day 1

Study Day = (Date of Interest) – (Study Day 1)

In order to distinguish nominal visit names from duration defined in days, visit names will be referred to as "Day 15", "Day 29", etc., and "15 days" or "29 days", etc. will be used to define time intervals.

Overall time on study will be defined as the total number of days a participant is known to be followed on study calculated as follows:

Overall time on Study = (Last date on study) – (Date of first dose) +1

Last date on study is defined as the date of the latest visit or evaluation or telephone contact, or time of death from all available data for a given participant.

Disease duration is defined as time from age at symptom onset to age at informed consent.

## 3.2. Study Treatments

The main presentations of data will use the following groups:

Baseline characteristics displays for assessing sham and 232SM203 similarity.

(	CS3B	CS3B	2.	32SM203	
Shan	n control	rol Matched Sham control		50/28 mg nusinersen	Total
Baseline character	ristics, dispositio	n, exposure, time o	n study		
Matched CS3	В	232SM	203		
Matched CS3	B			Total	

Product: Nusinersen
Study: 232SM203

For summaries of post-baseline efficacy by visit/time

Matched CS3B	232SM203	
	12/12 mg	50/28 mg
Sham control	nusinersen	nusinersen

Primary and secondary endpoints analyses comparing sham and key adverse event displays

Matched CS3B	232SM203
_	50/28 mg
Sham control	nusinersen

For secondary endpoints comparing higher dose to 12/12 mg in 232SM203, safety and post baseline safety parameters:

	232SM203
12/12 mg	50/28 mg
nusinersen	nusinersen

## 3.3. Study Periods

The total study duration for each participant will be approximately 323 to 420 days

- Screening: 21 days
- Loading period: 64 days

- Maintenance period: 215 days
- Follow-up: 23 to 120 days

# 3.4. Key Derived Variables

Not applicable.

# **3.5. Stratification Factors and Subgroup Variables**

## **Stratification Factors**

Randomization was stratified as follows:

- For participants with infantile-onset SMA by disease duration:
  - $\leq 12$  weeks and
  - > 12 weeks

# **Subgroup Variables**

The following are defined as subgroups:

- Baseline CHOP INTEND (<= median, > median, median calculated 232SM203 ITT Set)
- Geographic region:
  - Asia-Pacific (Australia, China, Hong Kong, Japan, Lebanon, Saudi Arabia, South Korea, Taiwan, Turkey)
  - Europe (Belgium, France, Germany, Great Britain, Hungary, Italy, Poland, Russia, Spain, Sweden)
  - North America (Canada, United States)
  - o South/Central America (Brazil, Chile, Colombia, Mexico)

The main analyses for the primary endpoint and time to death and time to death or permanent ventilation for higher dose versus sham will be repeated for the subgroups: disease duration and baseline CHOP INTEND total score. Summaries of change from baseline in CHOP INTEND will be repeated for each of the three subgroups up to Day 183.

The main analyses for the change in CHOP INTEND to Day 302 and time to death and time to death or permanent ventilation will be repeated for subgroups: disease duration, baseline CHOP INTEND for the higher dose versus 12 mg comparison within 232SM203.

Summaries of change from baseline in CHOP INTEND by visit will be presented for each of the three subgroups for the higher dose versus 12 mg comparison within 232SM203.

## 3.6. Analysis Sets

## 3.6.1. Within 232SM203

#### The Safety Set

The Safety Set is defined as all participants who receive at least one dose of nusinersen; participants will be analyzed in the treatment group based on what they actually received.

#### The Intent-to-Treat (ITT) Set

The Intent-to-Treat (ITT) Set is defined as all participants who are randomized and receive at least one dose of nusinersen; participants will be analyzed in the treatment group to which they are randomized. This will be the primary population for the analysis of efficacy endpoints.

#### **Per Protocol Set**

A Per Protocol Set will include the subset of the ITT Set who have no significant protocol deviations that would be expected to affect efficacy assessments.

Significant protocol deviations will be determined prior to database lock and will include:

Participants who have an SMN copy number other than 2, participants who were greater than 7 months of age at Screening, age of onset of clinical sign >180 days, participants who had hypoxemia at baseline (< 96% at an altitude of < 1500 meters, < 92% at an altitude of 1500 to 2000 meters, or < 90% at an altitude > 2000 meters at Screening).

Participants who are on permanent ventilation or tracheostomy at Screening.

Participants who took experimental or approved agents for the treatment of SMA, including gene therapy, biological agent, or device, during the study. This includes marketed agents at experimental doses that are being tested for the treatment of SMA (oral albuterol/salbutamol, riluzole, carnitine, sodium phenylbutyrate, valproate, hydroxyurea, etc.).

Participants who had a previous diagnosis that would confound the data/conflict with SMA.

If participants have missed planned doses/sham but still completed study.

Product: Nusinersen	Statistical Analysis Plan
Study: 232SM203	Version: 3.0 Final

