## 2.2. Study Design

This 3-part study will evaluate the efficacy and safety of a high dosing regimen of nusinersen in approximately 145 participants. The study will be conducted at approximately 65 sites globally. Following the completion of this study, all eligible participants may elect to enrol in a separate long-term extension study (232SM302), pending study approval by ethics committees and the appropriate regulatory authorities. In regard to participants rolling over from Part B, this will be done without unblinding the participant's treatment group.

Part B will consist of a pivotal, double-blind, active-controlled treatment period with either 2 or 4 loading doses of nusinersen (for the 50/28 mg Group and Control Group, respectively) administered intrathecally followed by maintenance doses approximately every 4 months thereafter. Approximately 75 participants with infantile-onset SMA will be randomized in a 1:2 ratio to receive either the currently approved dosing regimen or a 50/28 mg dosing regimen.

In the Control Group, up to a total of 25 participants will receive 4 loading doses of 12 mg of nusinersen administered intrathecally (Days 1, 15, 29, and 64), followed by maintenance doses of 12 mg on Days 183 and 279 (and a sham procedure on Day 135).

Product: Nusinersen	Statistical Analysis Plan
Study: 232SM203	Version: 3.0 Final

In the 50/28 mg Group, up to a total of 50 participants will receive 2 loading doses of 50 mg of nusinersen administered intrathecally (Days 1 and 15) and 2 sham procedures on Days 29 and 64, followed by maintenance doses of 28 mg on Days 135 and 279 (and a sham procedure on Day 183). In order to maintain blinding sham procedures will be used as shown in the table below.

Arm	Dose 1	Dose 2	Dose 3	Dose 4	Dose 5	Dose 6	Dose 7
50/28 mg	D1	D15	D29	D64	D135	D183	D279
Group	(50 mg)	(50 mg)	(sham)	(sham)	(28 mg)	(sham)	(28 mg)
Control (12/12	D1	D15	D29	D64	D135	D183	D279
mg) Group	(12 mg)	(12 mg)	(12 mg)	(12 mg)	(sham)	(12 mg)	(12 mg)

Participants will remain at the clinic for at least 24 hours after each study treatment administration or sham procedure.

Randomization in Part B will be performed using interactive response technology (IRT) and the randomization will be stratified by disease duration as follows:

- $\leq$  12 weeks and
- > 12 weeks (time from age at symptom onset to age at informed consent)

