### Sensitivity Analyses

- In order to test sensitivity of data handling for withdrawals not due to death, ranking criteria will be adjusted in the JRT for withdrawals not due to death.
- In order to test if permanent ventilation should be considered in evaluation of endpoint, ranking criteria will be adjusted for JRT to consider permanent ventilation in evaluation.
- The MI model will be run for total score for the ITT population excluding data from any subjects who died.
- Rank based implementation of joint rank method + MI.
- The main analysis will be repeated incorporating Jump to reference in the MI step.
- The main analysis will be repeated using PPS set.

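### Both Part B per-protocol definitions exclude participants who missed a dose or sham only if they completed the study, so membership depends on a post-randomisation outcome

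*SAP*

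**What the plan says.** The Part B infantile-onset SAP (section 3.6.1, Per Protocol Set) defines the set as ITT participants with "no significant protocol deviations that would be expected to affect efficacy assessments". The deviations are introduced by "Significant protocol deviations will be determined prior to database lock and will include", and the last item reads "If participants have missed planned doses/sham but still completed study". The later-onset SAP (section 3.5.1) has the same line. Neither list has an item for participants who missed a procedure and did not complete the study.

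Section 2.2 of the infantile-onset SAP schedules seven procedures in each arm. The 50/28 mg group has "2 sham procedures on Days 29 and 64" "and a sham procedure on Day 183", so three shams and four active doses. The 12 mg group has six active doses "and a sham procedure on Day 135", so one sham.

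Under section 6.1 of the infantile-onset SAP, assessments made after missed doses, or after stopping treatment, are analysed as observed. Scores missing for reasons other than death are multiply imputed, and such participants rank above all deaths.

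For the infantile-onset 50/28 mg versus 12 mg comparison, section 6.4.4 states "The main analysis will be repeated using PPS set" for Day 302 CHOP INTEND (also a row in Table 9). The tables in sections 6.4.9 and 6.4.10 carry a per-protocol row too. The later-onset SAP repeats its HFMSE, RULM and WHO milestone analyses on the set.

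**The concern.** A per-protocol analysis should show the dose comparison in participants treated as planned. Here the deviation that bears most directly on treatment received counts only if the participant later completes. Completion happens after randomisation and may depend on treatment and on how the infant is doing. Two participants with the same missed procedure are classified differently because of something that came afterwards, and the one removed is the one with observed data. That weakens the set as a check on the ITT result. The later-onset arms are planned at only 16 and 8, so one or two participants can move the estimate.

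A smaller question is whether a missed sham belongs in the rule, since it changes no drug exposure.

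**Working it through.** **1. The rule applied to three hypothetical infants in the 50/28 mg versus 12 mg comparison**

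| | Procedures | Study status | Day 302 score | Set as written | Set under the fix |
|---|---|---|---|---|---|
| A | Misses Day 135 | Completes | Observed | Out | Out |
| B | Misses Day 135 | Withdraws after Day 183 | Imputed | In: no listed item applies | Out |
| C | Has all that fall due | Withdraws after Day 183 | Imputed | In | In |

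As written, A and B share a deviation but are separated, while B and C differ in adherence but are treated alike. The fix removes both anomalies.

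**2. Procedure counts (section 2.2)**

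50/28 mg: 4 active + 3 sham = 7. 12 mg: 6 active + 1 sham = 7. The ITT definition requires at least one dose. Taking this as the Day 1 dose, six procedures can still be missed in each arm: 3 active + 3 sham, and 5 active + 1 sham.

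**3. Chance that a completer is excluded**

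Neither SAP gives a miss rate. Assume each procedure is missed independently with probability q = 2% to 5%, equal in both arms, and that one miss is enough (the line states no number).

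Any miss, either arm: 1 − (1 − q)^6.
- q = 2%: 1 − 0.98^6 = 11.4%. If all complete: 5.7 of 50 and 2.9 of 25.
- q = 5%: 1 − 0.95^6 = 26.5%. If all complete: 13.2 of 50 and 6.6 of 25.

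The chance of exclusion is the same in both arms.

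**4. Participants like B**

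The SAPs give no expected withdrawal rate. For scale only, the trimmed-mean example in section 6.1 supposes 4 of 50 and 5 of 25 died or withdrew. Applying the step 3 probabilities:
- 50/28 mg: 4 × 0.114 = 0.5 to 4 × 0.265 = 1.1.
- 12 mg: 5 × 0.114 = 0.6 to 5 × 0.265 = 1.3.

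These overstate somewhat, because an early leaver has fewer than six procedures due. They understate if those who leave miss more.

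**5. Excluded for a missed sham alone, every active dose received**

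50/28 mg: (1 − q)^3 × [1 − (1 − q)^3]. 12 mg: (1 − q)^5 × q.
- q = 2%: 0.9412 × 0.0588 = 5.5% (2.8 of 50) v 0.9039 × 0.02 = 1.8% (0.5 of 25).
- q = 5%: 0.8574 × 0.1426 = 12.2% (6.1 of 50) v 0.7738 × 0.05 = 3.9% (1.0 of 25).

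**6. If shams were simply struck from the rule**

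50/28 mg: 1 − (1 − q)^3. 12 mg: 1 − (1 − q)^5.
- q = 2%: 5.9% v 9.6%.
- q = 5%: 14.3% v 22.6%.

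**The case against.** **The list may be open.** Its opening phrase does not say it is exhaustive, so a participant like B could still be classified under the general condition. That is possible, but the only line on missed procedures names completers, which gives no stated basis for treating anyone else the same way.

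**The completion wording has a sensible purpose.** It plausibly stops deaths and withdrawals from being excluded merely because later procedures were never given, and the joint rank test needs the deaths. This stands as a purpose and the fix keeps it. The wording still does not separate procedures missed before leaving from those that fell due afterwards.

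**The impact is small.** This stands. The infantile-onset primary and ranked tests use the Matched Sham or ITT Set, and the later-onset use is also sensitivity only.

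**A reader might infer that the rule penalises the 50/28 mg arm**, because that arm has three shams against one. The documents do not support this. The rule counts doses and shams alike and each arm has seven procedures, so equal miss rates give equal total exclusion (step 3). Only the reason for exclusion differs by arm (step 5).

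**A reader might also conclude that shams should just be deleted from the rule.** That would move exclusions towards the 12 mg arm (step 6). Significant deviations are also settled before database lock in a double-blind part. On Days 29, 64, 135 and 183 one arm receives drug and the other sham, so sorting missed doses from missed shams would reveal the arm. Counting them together allows a blinded decision.

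**Conclusion.** The criterion is badly conditioned in both Part B SAPs and should be corrected. Read literally, it excludes completers with a missed procedure and observed scores, and retains participants who missed the same procedure on study and then withdrew. The consequence is confined to per-protocol sensitivity analyses.

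Under an independent, equal miss rate of 2% to 5%, which is an assumption, the line excludes 11.4% to 26.5% of completers in either arm. With the SAP's hypothetical count of deaths and withdrawals, roughly one participant per infantile-onset arm would be kept inconsistently. Actual numbers depend on miss and withdrawal rates that the documents do not give.

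The sham question is secondary. A missed sham fits the set's own test poorly, since it delivers no drug. Sham-only exclusions would be about three times as frequent per participant in the 50/28 mg arm (5.5% to 12.2% v 1.8% to 3.9%). This does not amount to a bias against that arm in total exclusions.

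**What to change.** In section 3.6.1 of the infantile-onset SAP and section 3.5.1 of the later-onset SAP, replace the line with:

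*Participants who missed a planned procedure (dose/sham) that fell due before the analysis visit while they were on study, whether or not they completed the study.*

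Procedures falling due after death or withdrawal then do not count. The limit must be time on study: a rule that counted every dose due while the participant was alive would exclude every living participant who withdrew before the Day 279 dose. The last procedure precedes Day 302, so one set serves all the Day 302 analyses. The wording also makes explicit that one miss is enough.

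On shams, the sponsor should either justify counting a missed sham as a deviation affecting efficacy, or keep the blinded rule and examine sham-only exclusions after unblinding.

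The cost is one line in each of two SAPs. The classification can still be made blinded before lock, from dosing and deviation records that the SAPs already plan to list. The small downside is that the set loses the few participants who missed a procedure and later withdrew or died.

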## 3.6.2. External data

For CS3B, the efficacy set at Day 183 and Day 302 as defined for the final analysis of CS3B will be utilized.

The following table describes analysis sets for the historical data and how they will be referenced in the remainder of the document.

Table	1:	Analy	sis	set
-------	----	-------	-----	-----

Analysis Set Label	Description
CS3B Day 183 efficacy set	This is the 'Evaluable set for Day 183' referenced in the Final CS3B CSR. It consists of N=37 sham control and N=73 12 mg nusinersen participants.
CS3B Day 302 efficacy set	This is the 'Evaluable set for Day 302' referenced in the Final CS3B CSR. It consists of N=28 sham control and N=49, 12 mg nusinersen participants.
Matched Sham Set	Analysis set for main comparisons of higher dose versus sham control.
	Subset of the 37 sham control participants in the CS3B Day 183 efficacy set similar to higher dose 232SM203 participants and all higher dose participants in the ITT set.
Matched Sham Set (sensitivity)	Subset of the 37 sham control participants in the CS3B Day 183 efficacy set similar to all N=75 232SM203 participants in the ITT set.
Greedy matched set (sensitivity)	Set of CS3B sham and 232SM203 higher dose participants matched by greedy matching. Note that not all higher dose participants will have a match.

Page 20

Product: Nusinersen	Statistical Analysis Plan
Study: 232SM203	Version: 3.0 Final

## 4. List of Planned Study Analyses

## 4.1. Interim Analysis

No interim analysis is planned. The unblinding plan details the steps to ensure that the blind is maintained throughout the entire study.

## 4.2. Primary Analysis

The primary analysis is to test the mean change in CHOP INTEND total score from baseline to Day 183 for the 50/28-mg in 232SM203 compared to the CS3B matched sham control Group, using the joint-rank test and handling drop out not due to death with multiple imputation.

## 4.3. Final Analysis

The final analysis will be performed when all infantile onset participants in Part B have completed the follow-up period.

# 5. Statistical Methods for Planned Analyses

Within the infantile-onset population to control the overall type 1 error at a 2-sided alpha level of 0.05, a sequential testing procedure ranked in the order of the primary and secondary endpoints will be utilized. Table 2 summarizes the planned statistical testing. Inferential conclusions about each successive analysis require statistical significance of the prior one.

Rank	Endpoint	Comparison Higher dose to:	Population	Description
1	Change from baseline to Day 183 in CHOP-INTEND total score	CS3B Sham control	Matched Sham Set	Primary
2	Proportion of HINE Section 2 motor milestone responders at Day 183	CS3B Sham control	Matched Sham Set	Secondary
3	Change from baseline to Day 183 in HINE Section 2 total score	CS3B Sham control	Matched Sham Set	Secondary
4	Change from baseline to Day 183 in plasma NF-L	CS3B Sham control	Matched Sham Set	Secondary

 Table 2:
 Sequential Testing Procedure for Primary and Secondary endpoints

#### Product: Nusinersen

#### Study: 232SM203

Statistical Analysis Plan Version: 3.0 Final

Rank	Endpoint	Comparison Higher dose to:	Population	Description
5	Change from baseline to Day 302 in CHOP-INTEND total score	232SM203 12 mg	ITT set	Secondary
6	Change from baseline to Day 302 in HINE Section 2 total score	232SM203 12 mg	ITT set	Secondary
7	Change from baseline to Day 64 in plasma NF-L	232SM203 12 mg	ITT set	Secondary
8	Time to death or permanent ventilation	CS3B Sham control	Matched Sham Set	Secondary
9	Time to death	CS3B Sham control	Matched Sham Set	Secondary
10	Time to death or permanent ventilation	232SM203 12 mg	ITT set	Secondary
11	Time to death	232SM203 12 mg	ITT set	Secondary

## 5.1. General Principles

Descriptive summary statistics will be presented for all primary, secondary **continuous** endpoints collected. Unless otherwise specified, for continuous endpoints, the summary statistics will generally include number of participants with data, mean, standard deviation, median, 25th percentile, 75th percentile, minimum and maximum. For categorical endpoints, the summary statistics will generally include number of participants with data, and the percentage of those with data in each category.

All summaries and listings will be presented by study groups unless otherwise specified. Visits in listings will be displayed as per CRF data collection rather than analysis visits.

The statistical software, SAS®(Version 9.4) will be used for all summaries and statistical analyses.

## Visit Windows for Early Withdrawal, Unscheduled Visits

Data from early withdrawal visits, post baseline unscheduled assessments will be assigned to an appropriate scheduled post baseline visit using a windowing scheme for assessments that are tabulated or summarized by visit. Scheduled visits will not be windowed.

The visit windowing will be performed for efficacy and safety endpoints.

For safety endpoints the following windows will be utilized.

Visit	Lower Bound	Upper Bound	Target Day
Baseline			<=2
Day 15	2	21	15
Day 29	22	47	29
Day 64	48	99	64
Day 135	100	159	135
Day 183	160	232	183
Day 279	233	290	279
Day 302	291	348	302

#### Table 3: Visit windows for safety Endpoints in 232SM203.

For efficacy endpoints, if the actual study day falls within: +/- 7 days of scheduled post baseline loading dose visits and +/-14 days of a maintenance dose then it will be considered for windowing.

The following rules will be implemented for windowing of these visits for both safety and efficacy.

- If more than one observation is within the same window, data from the regular scheduled visit will be used for that visit.
- If neither of the observations are from a regular scheduled visit the observation closest to the planned target date will be used. However, if both the observations are equidistant from the target date, the latest one will be used; if repeated measurements are on the same day, then the last measurement will be used.
- If windowing safety data and there is more than one observation in a window for a dosing visit the observation on the day of dosing will be chosen over the observation where dosing did not occur on the same day.
- In windowing laboratory data, if a central and local result is available within the window then the central laboratory result will be chosen.

Product: Nusinersen	Statistical Analysis Plan
Study: 232SM203	Version: 3.0 Final

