### 7.1.3. Clinical laboratory data

Laboratory data will be evaluated to determine the incidence of abnormalities that emerge during the course of the study. Changes in laboratory evaluations will be presented relative to baseline, which is defined as the closest visit prior to the first dose.

The following clinical laboratory parameters are to be assessed:

Hematology panel: complete blood count with differential and platelet count (hematocrit, hemoglobin, platelets, red blood cell count [RBC], white blood cell count [WBC], basophils, eosinophils, lymphocytes, monocytes, neutrophils)

Blood chemistry panel: albumin, total bilirubin, direct and indirect bilirubin, alkaline phosphatase, alanine aminotransferase (ALT) (SGPT), aspartate aminotransferase (AST) (SGOT), gamma-glutamyl transferase (GGT), sodium, potassium, calcium, chloride, phosphate, blood urea nitrogen (BUN), creatinine, cystatin, creatine phosphokinase, creatine kinase, bicarbonate (CO2), glucose, total protein.

Urinalysis: specific gravity, pH, protein, glucose, ketones, bilirubin, blood, red blood cells, white blood cells, epithelial cells, bacteria, casts and crystals

Urine total protein assessed by local laboratories CSF analysis: RBC, WBC, protein, glucose.

Coagulation: PT (prothrombin time), aPTT (activated partial thromboplastin time), and INR (international normalized ratio).

Each hematology, blood chemistry, coagulation and CSF laboratory parameter will be flagged as "low", "normal" or "high" relative to the parameter's normal range or as "unknown" if no result is available.

For each urinalysis laboratory parameter, the number and percentage of subjects experiencing postdose shifts to abnormal will be summarized.

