#### Table 2: Visit windows for safety Endpoints in 232SM203

Product: Nusinersen		Statistical Analysis Plan	
Study: 232SM203			Version: 1.0
Day 135	100	159	135
Day 183	160	232	183
Day 279	233	290	279
Day 302	291	348	302

For efficacy endpoints, the actual day of the unscheduled or end of study visits will be considered.

For post baseline visits up to and including Day 64 a +/-7 day window will be used and for visits between Day 135 and Day 302 a +/-14 day window will be used.

The following rules will be implemented for windowing:

- If more than one observation is within the same window, data from the regular scheduled visit will be used for that visit.
- If neither of the observations are from a regular scheduled visit the observation closest to the planned target date will be used. However, if both the observations are equidistant from the target date, the latest one will be used; if repeated measurements are on the same day, then the last measurement will be used.
- If windowing safety data safety data and there is more than one observation in a window for a dosing visit the observation on the day of dosing will be chosen over the observation where dosing did not occur on the same day.
- In windowing laboratory data, if a central and local result is available within the window then the central laboratory result will be chosen.

Study	Windowing
CS4	All dosed subjects will be included, and the Month 6 and Month 9 values collected will be utilized.
CS11	All dosed subjects meeting the re-evaluated conditions will be included. The protocol defined Day 265 visit will be used. If this was not collected since the subject moved to MMDR dosing, then Day 265 will be missing.
PMS study	The HFMSE visit data will be windowed to give Month 9 as study day 274 +/- 15 days. Therefore, study days between 259 and 289 will be considered, if >1 lie in the window the one closest to Day 274 will be selected. If two are equally close, the latest one will be selected.

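### The infantile-onset efficacy windows are tied to doses, so off-schedule assessments near Day 302 cannot be assigned to it; in the later-onset SAP the Day 279 and Day 302 windows overlap

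*SAP*

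**What the plan says.** **Infantile-onset SAP, section 5.1 (visit windows).** Data from early-withdrawal and unscheduled assessments are mapped to a scheduled post-baseline visit. Scheduled visits are left as they are. For efficacy, an assessment qualifies if it lies within plus or minus "7 days of scheduled post baseline loading dose visits and +/-14 days of a maintenance dose then it will be considered for windowing". No other visit type is named.

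**Infantile-onset SAP, sections 2.2 and 3.3.** The 50/28 mg group has loading doses "followed by maintenance doses of 28 mg on Days 135 and 279 (and a sham procedure on Day 183"). The control group has "maintenance doses of 12 mg on Days 183 and 279 (and a sham procedure on Day 135"). Section 3.3 gives a 64-day loading period, then "Maintenance period: 215 days", then at least 23 days of follow-up.

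**Infantile-onset SAP, section 5, Table 2.** Rank 5 is "Change from baseline to Day 302 in CHOP-INTEND total score" against 12 mg in the ITT set. Rank 6 is the same comparison for the HINE Section 2 total score.

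**Infantile-onset SAP, Table 3.** Under "For safety endpoints the following windows will be utilized", Day 302 runs from 291 to 348, Day 279 ends at 290, Day 15 starts at Day 2, and the Baseline row carries <=2 in the target-day column. Section 7.1.3 takes laboratory baseline as the value "which is defined as the closest visit prior to the first dose".

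**Later-onset SAP, section 4.4.** Visits up to Day 64 have a 7-day window either side, and "for visits between Day 135 and Day 302 a +/-14 day window will be used".

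**The concern.** Day 302 is an efficacy endpoint visit but not a dosing visit, so a rule that builds windows around doses leaves it out. The omission looks unintended: the same SAP's safety table and the later-onset efficacy rule both give Day 302 a window.

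Take an infant who leaves the study on Day 298 with a completed CHOP INTEND, recorded as an early-withdrawal visit. Read as written, the score cannot be assigned to Day 302, so the infant has no endpoint value and one is imputed (section 6.1). An assessment on Days 288 to 293 would be labelled Day 279, and would lose there to any scheduled Day 279 assessment. Ranks 5 and 6 are the first two comparisons with 12 mg, and ranks 7 to 11 can be claimed only if both succeed.

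In the later-onset SAP, Day 302 is the main analysis time point for HFMSE and RULM (section 5.1.5). An off-schedule assessment in the overlap could go to either visit, at the programmer's choice.

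**Working it through.** The plan states no figure to reproduce. The check lists each window as target day minus and plus the allowed half-width, then looks for gaps and overlaps by study day.

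**Where Day 302 lies.** Loading plus maintenance is 64 + 215 = 279, and adding the minimum follow-up gives 279 + 23 = 302. Day 302 is therefore in follow-up, 23 days after the last dose.

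**Efficacy windows.** Days 135 and 183 are treated as maintenance visits in both arms, although each is a sham procedure in one arm.

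| Visit | Half-width | Infantile-onset | Later-onset |
|---|---|---|---|
| Day 15 | 7 | 8-22 | 8-22 |
| Day 29 | 7 | 22-36 | 22-36 |
| Day 64 | 7 | 57-71 | 57-71 |
| Day 135 | 14 | 121-149 | 121-149 |
| Day 183 | 14 | 169-197 | 169-197 |
| Day 279 | 14 | 265-293 | 265-293 |
| Day 302 | 14 (later-onset only) | none | 288-316 |

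**Gap, infantile-onset.** Day 302 is in no window. A 14-day rule would cover Days 288 to 316, which is 29 days. Of these, 288 to 293 (6 days) currently go to Day 279 and 294 to 316 (23 days) go nowhere.

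**Overlap, later-onset.** 279 + 14 = 293 and 302 - 14 = 288, so Days 288 to 293 (6 days) are in both windows. The tie rules settle several observations in one window, not one observation in two.

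**Shared Day 22, both SAPs.** 15 + 7 = 22 and 29 - 7 = 22. The day is 7 days from each target, so closeness does not settle it.

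**Natural split.** The midpoint of 279 and 302 is 290.5. Day 290 is 11 days from 279 and 12 from 302; Day 291 is 12 from 279 and 11 from 302. Both Part B safety tables already divide at 290/291.

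**Safety Baseline, infantile-onset.** Baseline <=2 and Day 15 from Day 2 share exactly Day 2; every other pair of adjacent safety windows is contiguous. Study Day 1 is the date of first dose, so Day 2 is after dosing. The later-onset and Part C tables have <=1.

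**Weight of one participant.** 1/25 = 4% of the planned infantile 12 mg arm, and 1/8 = 12.5% of the planned later-onset control arm. This is the share one child represents, not an estimated effect on any result.

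**The case against.** The strongest reply is that windowing applies only off schedule. A Day 302 visit done as scheduled enters ranks 5 and 6 unchanged, so it would be misleading to say that Day 302 has no usable data. The infantile-onset safety sections also treat the last visit as a combined Day 302/ET visit. Whether a Day 298 assessment would be recorded as scheduled or as early withdrawal depends on the protocol's visit window and the CRF, which are not at hand. This stands and limits the impact. It does not remove the gap, because section 5.1 sends early-withdrawal visits through windowing.

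Three stronger readings are tempting and are not supported.

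- **Day 2 safety results would count as baseline and drop out of the abnormality counts.** Section 5.1 sends post-baseline unscheduled data only to post-baseline visits. Sections 7.1.3 and 7.1.6 fix laboratory and vital-sign baselines before the first dose. Laboratory shifts (7.1.3), ECG abnormalities (7.1.5) and vital-sign abnormalities (7.1.6) use all post-baseline data, scheduled or not. The <=2 entry is only a table inconsistency.
- **The affected infant is ranked below every completer in a confirmatory test.** That ranking belongs to the sensitivity analysis for withdrawals not due to death (sections 6.1 and 6.4.4). In the main analysis the infant's value is imputed.
- **The primary endpoint loses its window because Day 183 is a sham in the 50/28 mg group.** The wording permits arm-specific windows if read literally. However, the dosing table in section 2.2 numbers Days 135 and 183 as Dose 5 and Dose 6 in both arms, so a window by visit is the more natural reading. On that reading the endpoints at Days 64 and 183 are covered.

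The later-onset overlap concerns a 24-participant cohort whose size has no statistical basis, and that SAP sets out no hierarchical testing sequence. Extending its closest-to-target rule across windows would resolve Days 288 to 293, but the SAP writes that rule only for observations competing within one window.

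**Conclusion.** The point holds as a gap in the assignment rules, with small expected impact. In the infantile-onset SAP, off-schedule efficacy assessments from Day 294 have no visit and those on Days 288 to 293 go to Day 279. An observed score close to the endpoint of ranks 5 and 6 could then give way to an imputed one. In the later-onset SAP, six days belong to two visits with no rule to choose between them, and Day 22 is shared by two visits in both SAPs.

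The conclusion assumes that section 5.1 is applied as written and that the assessment is recorded as early withdrawal or unscheduled. The documents give no count of such assessments, so no shift in any estimate can be calculated. The case for acting is that the SAP, not a programming decision, should fix which endpoint data are used.

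**What to change.** - **Infantile-onset SAP, section 5.1:** replace the dose-based sentence with a list of efficacy windows by visit, the same for both arms: Day 64 = 57-71, Day 135 = 121-149, Day 183 = 169-197, Day 279 = 265-290, Day 302 = 291-316. This also removes the doubt about sham days.
- **Later-onset SAP, section 4.4:** use the same 290/291 split for Days 279 and 302.
- **Both SAPs:** give Day 22 to one visit. Placing it with Day 29 (Day 15 = 8-21, Day 29 = 22-36) would match the safety tables, where the Day 29 window starts at 22.
- **Infantile-onset SAP, Table 3:** change Baseline from <=2 to <=1, as a consistency correction. Keep the plasma NF-L fallback to a post-dose sample within Day 2 (section 6.4.3) as its own stated exception.

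The cost is a few lines of text and a matching change to the windowing program, with no new data. The edits should be made without reference to outcomes, and the report should give the number of assessments whose visit assignment depends on them.
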